BUN, as standard of care (will not be repeated if done within 8 (+/- 3 days) days before the start of treatment). During treatment, an earlier evaluation will be performed if clinically indicated.

- d. Radiological evaluation may include CT of the chest and abdomen, Ultrasound, bone Scan and X-Rays, brain MRI as clinically indicated for standard of care. PET/CT, Chest wall/breast photos, EKG and ECHO or MUGA may also be performed as indicated for standard of care. During treatment, an earlier evaluation will be performed if clinically indicated. The same method of evaluation, specific to the subject's condition, will be performed according to the time points.
- e. Peripheral blood and serum for correlative studies. Approximately 50cc of blood will be drawn at baseline, cycle 3rd, 6th, 9th, then every 2 cycles (i.e.11th, 13th, 15th, etc.) and at disease progression.
- f. The mandatory Safety Follow-Up Visit should be conducted approximately 30 days after the last dose of trial treatment or before the initiation of a new anti-cancer treatment, whichever comes first. All AEs that occur prior to the Safety Follow-Up Visit should be recorded. Safety Follow-Up Visit can be done in the clinic, or by phone if patient is not willing to come to the clinic for follow up.
- g. 3 months follow up can be performed in the clinic, or by phone if patient is not willing to come to the clinic for follow up.
- h. Optional biopsy at disease progression.
- i. TSH, Free T4 and Total cortisol will be monitored at baseline, every other cycle during Cycle 1-8 and every cycle for Cycle 9 and beyond as standard of care.
- j. Cycle 1-8 are defined as 3 weeks per cycle, Cycle 9 and beyond are defined as 6 weeks per cycle, pembrolizumab (200mg or 400mg) will be given on Day 1 of each cycle as section 4.2.
- k. registration

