6.2.2 Blood samples

Collection and processing

Multiple blood draws will be required for this trial. All blood tubes will be labeled only with the patients' unique study number. Approximately 100cc will be drawn for each immunologic assessment (at baseline; prior to dosing of study drug with every third cycle i.e. cycle 3, 6, 9, 12 etc , or every other cycle after for patients who start Pembrolizumab 400mg at C9 and beyond; and at disease progression). 10cc will be collected into a BD Vacutainer Rapid Serum tube (BD, Franklin Lakes, NJ) which contains a clot activator and silicone coated interior. After

centrifugation, serum will be collected, aliquoted in 1cc vials and frozen. 70cc will be collected into BD Vacutainer CPT Cell Preparation tubes which contain an anticoagulant (sodium heparin or sodium citrate) with FICOLL HYPAQUE density gradient fluid and a polyester gel barrier. The density gradient fluid and the gel barrier allow for the separation of peripheral blood mononuclear cells (PBMC) from the red blood cells by a single step centrifugation process. The PBMC fraction will be collected by centrifugation and suspended in RPMI-1640 (GIBCO, Invitrogen Corporation, Carlsbad, CA) with 10% FCS (Gemini Bio-Products, West Sacramento, CA) and antibiotics. Plasma will be collected from CPT Cell Preparation tubes and stored. 20cc blood will be collected in heparin 10ml green top tubes for FACS assay.

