6.2.3 Assays

Serum

- Soluble factors such as cytokines and chemokines present in serum collected at baseline, during, and after treatment will be quantified using a multiplex assay which has the capability to simultaneously measure multiple analytes from a single sample. Factors to be evaluated may include but not necessarily be limited to IFN- γ , TNF- α , IL-2, IL-4, IL-5, IL-7, IL-10, IL-12, IL-15 and IL-17.
- Additional immunoassays will be performed to quantify soluble receptors present in the serum. Analyses may include but not necessarily be limited to soluble CD25, soluble PD-1, and soluble LAG-3.

Peripheral blood mononuclear cells

- The proportion of specific lymphocyte subsets to include T cells, B cells, and the proportion of memory and effector T cell subsets will be quantified by flow cytometry.
- The expression levels of T cell co-stimulatory and co-inhibitory markers including but not necessarily limited to PD-1, PD-L1, other B7 family members, and ICOS will be quantified by flow cytometry.

Plasma

- Exosomal RNA-sequencing will be performed with RNA extracted from plasma by Insight Genetics, Inc along with the tumor sample listed in section 6.2.1. There is only one time point plasma sample needed, and plasma samples at baseline will be preferred, but samples collected at other time points can be substitute if the baseline sample is unavailable.
- Plasma will be stored for future research purpose.

FACS assay

- Intracellular cytokine synthesis by T-cells activated through the T-cell receptor (TCR).
- Cytokine production by dendritic cells activated with Toll-like receptor (TLR) agonist.

- The NK cell assay.

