7.0 STATISTICAL ANALYSIS PLAN

The primary objective of this phase II trial is to assess the efficacy of MK-3475 as a single agent in metastatic IBC and non-IBC TNBC patients. The primary endpoint is the rate of disease control measured at the end of 4 months from the start of therapy.

The disease control rate is defined as the percentage of patients either 1) with measurable disease that achieve iCR, iPR, iSD, or 2) with non-measurable disease that achieve iCR or iSD, , by 4 months or more in all evaluable patients. We will also perform secondary analysis on intent-to-treat patient population where those patients who drop out early will be considered as progression.

The trial will be conducted using Simon's optimal two-stage design and the rate of disease control will be estimated accordingly. It is assumed that the MK-3475 single agent will have a disease control rate of 30%. A disease control rate of 10% or lower will be considered treatment failure and the regimen will be rejected under this circumstance. When the probability of accepting a "bad" regimen (i.e. disease control rate 10% or lower) is 0.10 and the probability of rejecting a "good" regimen (i.e. disease control rate 30% or higher) is also 0.10, Simon's optimal 2-stage design requires 12 patients enter in the first stage. The study accrual will be delayed until all 12 patients are evaluable for disease control status. If 1 or no patients maintain disease control on treatment, the trial will be stopped and the regimen will be declared as ineffective. If 2 or more patients maintain disease control, 23 more patients will be enrolled to the study to reach a total of 35 treated patients. By the end of the study, the new regimen will be rejected if rate of disease control is less than or equal to 5/35 and will be considered worthy of further investigation otherwise.

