Various biomarker endpoints will be measured in various specimens. Correlation among biomarkers at baseline in each specimen and between different specimens will be assessed. The association among various continuous and discrete biomarkers or disease status groups will be assessed by the exploratory data analysis using scatter plot matrix, box plots, BLIP plot³⁷ and trellis plot, etc, and may be tested by t-test/ANOVA/Wilcoxon rank sum test/Kruskal-Wallis test, whichever is appropriate. Correlation between continuous biomarkers will be examined by Pearson or Spearman rank correlation coefficients. The association between discrete biomarkers will be tested by chi-square or Fisher's exact test. Paired t-test/Wilcoxon rank sum test and McNemar's test may be used to test the change of a single continuous biomarker and discrete biomarker, respectively, over time within each treatment group. Repeated measures analysis including mixed effects model will be performed to analyze the correlation between disease control and biomarkers change over time.³⁸ Disease control survival and overall survival time from the registration date will be estimated using Kaplan-Meier method.

All statistical tests will be performed at a two-sided significance level of 5% using SAS or S-Plus, as appropriate.

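### The mixed model of disease control against biomarker change (section 7.0) does not restrict which samples enter, although samples at progression and after month 4 depend on the outcome

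*Combined protocol and SAP*

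**What the plan says.** Section 7.0 commits to the analysis: "Repeated measures analysis including mixed effects model will be performed to analyze the correlation between disease control and biomarkers change over time". Tests are two-sided at 5%. The section gives no sample window, no coding of time and no rule for samples taken at progression. It also does not say whether disease control here means status at month 4 or status at each visit. For the primary endpoint it is a single status: "The primary endpoint is the rate of disease control measured at the end of 4 months from the start of therapy".

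The sampling is set out elsewhere:

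- Section 5.0, footnote e: blood is "drawn at baseline, cycle 3rd, 6th, 9th, then every 2 cycles (i.e.11th, 13th, 15th, etc.) and at disease progression".
- Section 6.2.2 ties scheduled draws to dosing, "prior to dosing of study drug with every third cycle i.e. cycle 3, 6, 9, 12 etc", moves to alternate cycles for patients on the six-weekly dose, and also adds a draw at progression.
- Section 5.0, footnote j: "Cycle 1-8 are defined as 3 weeks per cycle, Cycle 9 and beyond are defined as 6 weeks per cycle".
- Section 6.2.3: "Soluble factors such as cytokines and chemokines present in serum collected at baseline, during, and after treatment will be quantified using a multiplex assay".
- Section 4.5 ends treatment at progression or after 24 months. Section 6.2.1 makes on-study biopsies optional and limits them to progression.

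**The concern.** A patient who progresses early gives a baseline sample, perhaps one or two scheduled samples, and then a sample taken because of progression. A patient who stays controlled gives a long run of scheduled samples, and a progression sample only late. If all of these enter a model that compares trajectories by disease control, part of the difference in trajectory comes from the sampling rule. A marker that carries no information before progression, but moves when the tumor grows, could then be reported as tracking benefit.

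At stake is the reading of the exploratory biomarker objectives in section 2.2, chiefly the first, which looks for markers associated with efficacy.

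**Working it through.** **1. The plan's own figures.** The documents give no figure for the biomarker model. Sample size and rates come from the Simon designs in section 7.0. For 2/21 then 7/50, the probability of accepting the regimen is the sum over x = 3 to 21 of P(X1 = x) × P(X2 ≥ 8 − x), with X1 ~ Bin(21, p) and X2 ~ Bin(29, p). This gives 0.0979 at p = 0.10 and 0.9008 at p = 0.25. The 1/12 then 5/35 design gives 0.0977 at 0.10 and 0.9014 at 0.30. Both designs reproduce.

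**2. When samples fall.** Nominal weeks from the stated cycle lengths:

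- cycle 3: 2 × 3 = week 6
- cycle 6: 5 × 3 = week 15
- cycle 9: 8 × 3 = week 24
- cycle 11: 24 + 2 × 6 = week 36

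Four months is 17.39 weeks. Only baseline, cycle 3 and cycle 6 precede it.

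**3. Who is still giving scheduled samples.** Under an assumed constant hazard, S(t) = r^(t/17.39), where r is the month-4 rate:

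| r | week 6 | week 15 | week 24 |
|---|---|---|---|
| 0.25 | 62% | 30% | 15% |
| 0.10 | 45% | 14% | 4% |

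A patient still on treatment and free of progression at week 24 was controlled at month 4. Later scheduled draws therefore come almost only from that group.

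**4. False-positive rate.** The following are assumed and are not in the documents: exponential progression times matched to r, scans every 6 weeks, within-patient correlation 0.5, and a marker with no relation to month-4 status before progression. The marker shifts by 0, 0.5 or 1 residual SD in the progression sample. The model is random-intercept REML, and the test is the disease control × time interaction at 5%. There were 1,000 trials per scenario (844 to 862 usable at n=50, r=0.10).

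| n, r | All samples, linear time: 0 / 0.5 / 1 SD | All samples, post versus baseline: 0.5 / 1 SD | Scheduled pre-progression samples to month 4, categorical time: 1 SD |
|---|---|---|---|
| 50, 0.25 | 3.8 / 19.0 / 49.1% | 8.5 / 14.4% | 5.5% |
| 35, 0.25 | 4.5 / 13.0 / 37.0% | 6.3 / 8.7% | 4.2% |
| 50, 0.10 | 5.3 / 14.6 / 33.2% | 5.8 / 10.2% | 7.1% |
| 35, 0.30 | 5.6 / 17.0 / 37.6% | 7.7 / 9.7% | 5.2% |

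A separate run at n=50, r=0.25 gave about 16% and 46% with linear time, and 10% and 18% with the post-versus-baseline contrast. About 29% to 37% of samples in the table's scenarios were progression samples, and 10% to 22% fell after month 4.

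The mechanism is simple. The same shift arrives early in non-controlled patients and late in controlled ones. A straight line through a 1 SD change is steep over a short follow-up and shallow over a long one.

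**5. Why the time coding matters too.** Suppose there is no progression shift, but every patient's marker takes the same step once on drug. The all-samples linear model then gives 23% (0.5 SD step) and 65% (1 SD step) at n=50, r=0.25. Dropping only the progression samples still leaves about 10% to 44% across the scenarios with a step. Restricting to scheduled, pre-progression samples up to month 4 with categorical time gave 3.8% to 7.1% in every scenario, and about 4% to 9% in the separate run.

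**The case against.** The strongest reply is that the plan nowhere says the model will use every sample. Sections 5.0 and 6.2.2 are collection schedules, not analysis sets, and a careful analyst might exclude progression samples. It is true that a reader might infer a stated intention to use all on-study samples, and the text does not support that. What stands is that nothing excludes them, and the choice stays open until the data are seen.

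Second, the inflation is conditional. With no marker movement at progression and no common on-drug step, the mixed model keeps about 5%. With a post-versus-baseline contrast the excess is modest. Section 7.0 commits to neither form, so it does not secure the safer one.

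Third, a reader might expect a comparison of each patient's last sample with baseline to be badly inflated. It is not under this schedule. Controlled patients also give a progression sample when they later progress: at r = 0.25, only 0.25^6 = 0.02% would remain progression-free at 24 months. The shift then cancels, and simulated rates were 5.7%, 5.2% and 4.8% for shifts of 0.3, 0.5 and 1 SD. The point rests on the trajectory model the plan names, not on that contrast.

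Fourth, if disease control means status at each visit, a progression sample gives a legitimate concurrent association. That is correct, but it would not show that the marker predicts benefit. The plan should say which is meant.

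**Conclusion.** The concern holds as a gap in an exploratory analysis that can produce a false association. At n=50 and 25% controlled, a random-intercept model on all samples with linear time has a false-positive rate of about 5% with no progression shift, 16% to 19% with a 0.5 SD shift and 46% to 49% with a 1 SD shift. With a post-versus-baseline contrast the corresponding figures are 8.5% to 10% and 14% to 18%. These sizes rest on assumed shifts, a constant hazard, 6-weekly scans and a within-patient correlation of 0.5. They show what could happen and do not forecast this trial.

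A reader might go further and conclude that exploratory objective 1 as a whole is undermined. The documents do not support that. The objective also covers safety and tissue markers such as PD-L1, and section 7.0 plans baseline correlations and group comparisons that do not depend on this model. The primary endpoint, its confidence interval and the Simon boundaries are untouched. The priority is low, but the correction is cheap.

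**What to change.** Add to section 7.0 wording to this effect:

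> The association of biomarker change with month-4 disease control will use scheduled samples taken before progression and no later than month 4 (baseline, cycle 3, cycle 6), with time as a categorical factor. A sensitivity analysis will relate change from baseline to cycle 3 to month-4 status among patients free of progression at cycle 3. Samples taken at progression or after month 4 will be described separately.

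Define the window by date as well as cycle, because section 4.2.1 lets toxicity lengthen cycle intervals and a delayed cycle 6 could pass month 4. Footnote e and section 6.2.2 agree on cycles 3 and 6. They differ in how they word the draws from cycle 9 and in blood volume (50cc against 100cc), and should be reconciled.

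No new visits or samples are needed. The cost is fewer samples in this one analysis. With n=50 and r=0.25 under a constant hazard, about 0.62 × 50 = 31 patients would contribute at week 6 and 0.30 × 50 = 15 at week 15. Of those 15, about 12.5 (0.25 × 50) would be controlled patients, so most of the between-group information sits at cycle 3. Making the cycle-3 landmark the only analysis would discard cycle 6 without need. A landmark also leaves out patients who progress before week 6, which is 38% of patients at r=0.25 and 55% at r=0.10. That is why it is better as a sensitivity analysis.

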8.0 LABELING, PACKAGING, STORAGE AND RETURN OF CLINICAL SUPPLIES

8.1 Investigational Product

The investigator shall take responsibility for and shall take all steps to maintain appropriate records and ensure appropriate supply, storage, handling, distribution and usage of investigational product in accordance with the protocol and any applicable laws and regulations.

Clinical Supplies will be provided by Merck as summarized in Table 11.

Table 6 Product Descriptions

Product Name & Potency	Dosage Form
MK-3475 100 mg/ 4mL	Solution for Injection

8.2 Packaging and Labeling Information

Clinical supplies will be affixed with a clinical label in accordance with regulatory requirements.

8.3 Clinical Supplies Disclosure

This trial is open-label; therefore, the subject, the trial site personnel, the Sponsor and/or designee are not blinded to treatment. Drug identity (name, strength) is included in the label text; random code/disclosure envelopes or lists are not provided.

8.4 Storage and Handling Requirements

Clinical supplies must be stored in a secure, limited-access location under the storage conditions specified on the label.

Receipt and dispensing of trial medication must be recorded by an authorized person at the trial site.

Clinical supplies may not be used for any purpose other than that stated in the protocol.

8.5 Returns and Reconciliation

The investigator is responsible for keeping accurate records of the clinical supplies received from Merck or designee, the amount dispensed to and returned by the subjects and the amount remaining at the conclusion of the trial.

Upon completion or termination of the study, all unused and/or partially used investigational product will be destroyed at the site per institutional policy. It is the Investigator's responsibility to arrange for disposal of all empty containers, provided that procedures for proper disposal have been established according to applicable federal, state, local and institutional guidelines and procedures, and provided that appropriate records of disposal are kept.

9.0 DATA MANAGEMENT

Data collected from the study will be entered in REDCap database. The Principal Investigator is responsible for assuring that the data entered into the database are complete and accurate and that data entry is performed in a timely manner. Deidentified data will be shared with University of Hawaii Cancer Center (UHCC) for review and analysis.

9.1 Data collection for this study including:

- 1) demographic information (sex, race, and date of birth),

- 2) date of initial breast cancer diagnosis, pathology report of primary breast cancer, biomarker status, and date and location of distant metastases;
- 3) history of breast cancer surgery, and radiation therapy, if applicable;
- 4) date and type of chemotherapy and/or hormonal therapy for metastatic disease;
- 5) all AEs will be collected, however only ≥ 2 non-hematologic AEs and ≥ 3 hematological AEs will be recorded. Other abnormal laboratory values will not be reported as AEs; however, any clinical consequences of abnormality should be reported as AEs.
- 6) Concomitant medication will be recorded per standard of care in clinic database, and will not be recorded in the study database.

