4.3.1 Acceptable Concomitant Medications

All treatments that the investigator considers necessary for a subject's welfare may be administered at the discretion of the investigator in keeping with the community standards of medical care. Concomitant medication will be recorded as standard of care in clinic database.

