4.3.2 Prohibited Concomitant Medications

Subjects are prohibited from receiving the following therapies during the study.

- Any anti-cancer agents.
- Radiation therapy
 - Note: Radiation therapy to a symptomatic solitary lesion or to the brain will be allowed.
- Live vaccines within 30 days prior to the first dose of trial treatment and while participating in the trial. Examples of live vaccines include, but are not limited to, the following: measles, mumps, rubella, chicken pox, yellow fever, rabies, BCG, and typhoid (oral) vaccine. Seasonal influenza vaccines for injection are generally killed virus vaccines and are allowed; however intranasal influenza vaccines (e.g. Flu-Mist®) are live attenuated vaccines, and are not allowed.
- Glucocorticoids for any purpose other than to modulate symptoms of suspected immunologic etiology.

Subjects who, in the assessment by the investigator, require the use of any of the aforementioned treatments for clinical management should be removed from the trial. Subjects may receive other medications that the investigator deems to be medically necessary.

There are no prohibited therapies during the Post-Treatment Follow-up Phase.

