4.4 Rescue Medications & Supportive Care

Subjects should receive appropriate supportive care measures as deemed necessary by the treating investigator. Suggested supportive care measures for the management of adverse events with potential immunologic etiology are outlined below and in greater detail in the ECI guidance document (Appendix C in PDOL). Where appropriate, these guidelines include the use of oral or intravenous treatment with corticosteroids as well as additional anti-inflammatory agents if symptoms do not improve with administration of corticosteroids. Note that several courses of steroid tapering may be necessary as symptoms may worsen when the steroid dose is decreased. For each disorder, attempts should be made to rule out other causes such as metastatic disease or bacterial or viral infection, which might require additional supportive care. The treatment guidelines are intended to be applied when the investigator determines the events to be related to pembrolizumab.

Note: if after the evaluation the event is determined not to be related, the investigator is instructed to follow the ECI reporting guidance but does not need to follow the treatment guidance (as outlined in the ECI guidance document). Refer to Section 4.2.2 for dose modification.

It may be necessary to perform conditional procedures such as bronchoscopy, endoscopy, or skin photography as part of evaluation of the event. Suggested conditional procedures, as appropriate, can be found in the ECI guidance document (Appendix C in PDOL).

- **Pneumonitis:**

- For **Grade 2 events**, treat with systemic corticosteroids. When symptoms improve to Grade 1 or less, steroid taper should be started and continued over no less than 4 weeks.
- For **Grade 3-4 events**, immediately treat with intravenous steroids. Administer additional anti-inflammatory measures, as needed.
- Add prophylactic antibiotics for opportunistic infections in the case of prolonged steroid administration.

- **Diarrhea/Colitis:**
Subjects should be carefully monitored for signs and symptoms of enterocolitis (such as diarrhea, abdominal pain, blood or mucus in stool, with or without fever) and of bowel perforation (such as peritoneal signs and ileus).

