5.0 STUDY FLOW CHART

Trial Period:	Screening Phase	Treatment Cycles ^j								End of Treatment	Post-Treatment		Survival Follow Up ^k	
		1	2	3	4	5	6	7	8		If pt returns for follow up	Safety F/U ^f	Follow-Up ^g	
Treatment Cycle/Title:	Screening /Baseline									Cycle 9 and beyond				
Scheduling Window (Days):	Within 28 days	± 3	± 3	± 3	± 3	± 3	± 3	± 3	± 3			1 month after last dose	3 months after last dose	Annually for at least 5 years
Informed Consent	x													
Inclusion/Exclusion Criteria	x													
Demographics and Breast Cancer History ^a	x													
Concomitant Medication Review per SOC	x													
Physical Exam ^b , V/S	x	x	x	x	x	x	x	x	x	x	x			
Adverse Events ^b	x	x	x	x	x	x	x	x	x	x	x	x	x	
ECOG Performance Status ^b	x	x	x	x	x	x	x	x	x	x	x			
Pregnancy Test – Urine or Serum β-HCG (for women with childbearing potential)	x													
CBC and Biochemical Profiles ^c	x	x	x	x	x	x	x	x	x	x	x			
EKG, ECHO or MUGA as SOC ^d	x													
TSH, Free T4 and Totalcortisol ⁱ	x		x		x		x		x	x	x			
Radiological Evaluation as clinically indicated and as SOC ^d	x		x		x		x		x	x	x			
Archived biopsy or surgical specimens (block or unstained slides) obtained at any time prior to treatment.	x													
Correlative Studies Blood Collection ^e	x		x		x		x		x	x				
MK-3475 Administration		x	x	x	x	x	x	x	x	x				
Survival Status												x	x	
Optional biopsy at disease progression ^h											x			

- Demographics include patient's age, gender and race. Medical history includes primary breast cancer pathological diagnosis, ER/PR/HER2 status, and metastatic disease sites. prior therapies and procedures for breast cancer,
- Complete physical exam during the screening period. This will not be repeated if done within 8 (+/- 3 days) days before the start of treatment. During treatment, Physical Exam as clinically indicated prior to trial treatment administration. Adverse events and ECOG performance status assessment can be done within 8 (+/- 3 days) days before the start of treatment. Adverse events and ECOG will be assessed every 3 weeks either in the clinic visit or by calling through the end of treatment.
- Hematologic and biochemical profiles (CBC, albumin, alkaline phosphatase, ALT, AST, LDH, uric acid, calcium, glucose, phosphorus, potassium, sodium, magnesium, total bilirubin, total protein,

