9.2. Data confidentiality plan

All laboratory and clinical data gathered in this protocol will be stored in a password-protected database. All patient information will be handled using anonymous identifiers. Linkage to patient identity will be possible only after accessing a password-protected database. Access to the database will be available only to individuals directly involved in the study.

Information gathered for this study will not be reused or disclosed to any other person or entity, or for other research. Once the research has been completed, identifiers will be retained for as long as is required by law and by institutional regulations, and at that point will be destroyed.

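### Corticosteroid use is kept out of the study database, so immune samples drawn on steroids cannot be identified from it and may confound the exploratory on-treatment biomarker analyses

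*Combined protocol and SAP*

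**What the plan says.** Section 9.1 lists the data to be collected. Item 6 reads: "Concomitant medication will be recorded per standard of care in clinic database, and will not be recorded in the study database". Section 4.3.1 gives the same location: "Concomitant medication will be recorded as standard of care in clinic database". In the flow chart (Section 5.0), the row "Concomitant Medication Review per SOC" carries a single mark, at screening.

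Section 4.3.2 includes among the prohibited therapies "Glucocorticoids for any purpose other than to modulate symptoms of suspected immunologic etiology". Steroid use during treatment is thus confined to suspected immune-related events. Section 4.4 directs corticosteroids for pneumonitis, colitis, hypophysitis, hyperthyroidism, hepatic and renal events. Once the event has improved to Grade 1 or below, "steroid taper should be started and continued over no less than 4 weeks".

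Research blood is taken at baseline, before dosing at cycles 3, 6 and 9, at every second 6-week cycle after that, and at progression (Section 6.2.2; flow chart footnote e). Section 6.2.3 measures "The proportion of specific lymphocyte subsets to include T cells, B cells, and the proportion of memory and effector T cell subsets", together with serum cytokines and T-cell, dendritic-cell and NK-cell function. Exploratory objective 1 (Section 2.2) relates blood and tumor biomarkers to safety and efficacy. Section 7.0 adds: "Repeated measures analysis including mixed effects model will be performed to analyze the correlation between disease control and biomarkers change over time". Neither Section 6.2 nor Section 7.0 mentions steroid exposure at the time of a draw.

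**The concern.** The assays describe the state of the immune system, and exclusion criterion 2 itself groups systemic steroids with immunosuppressive therapy. A sample drawn during a steroid course may therefore reflect the steroid as well as MK-3475 and the disease.

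Steroid exposure is not spread at random over patients. By Section 4.3.2 it falls on those with suspected immune toxicity. If on-treatment samples are compared between patients with and without toxicity, the treatment of the toxicity can produce a difference that looks like a biomarker of it. The same samples enter the model of biomarker change against disease control. Anyone working from the study database alone has no medication variable with which to adjust or check. That would include the outside cancer center, if the de-identified data it receives come only from that database.

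**Working it through.** The plan states no figure on this point, so there is none to reproduce. The check traces the data flow and then illustrates how likely an overlap is.

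**1. Can the study database identify an on-steroid sample?**
- Medication: not in the study database (Section 9.1, item 6).
- Adverse events: non-hematologic events of Grade 2 or higher are recorded (Sections 6.3.1 and 9.1, item 5). Every corticosteroid trigger in Section 4.4 is Grade 2 or higher, so most steroid-treated events should leave an entry. The plan does not say that such an entry carries steroid start, stop or dose.
- Gap in that proxy: Section 4.4 includes steroids for Grade 2 hepatic events, while Sections 6.3.1 and 9.1 say that abnormal laboratory values are not reported as adverse events. Section 6.3.1 also says that clinically significant laboratory events are graded and recorded, so it is inconsistent on this.

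The answer is no, except in part and by inference.

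**2. Can a draw fall inside a steroid course?** For several toxicities, Table 2 (Section 4.2.2) allows study drug to restart at Grade 0-1. Section 4.4 starts the taper at Grade 1 or less, and the taper lasts at least 28 days. Table 2's discontinuation criterion refers to reducing the steroid to a stated level, not to stopping it. Draws are taken before dosing. A dose resumed during the taper, at a cycle with a scheduled draw, gives an on-steroid sample.

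**3. Illustrative overlap.** Draw times follow from the cycle lengths:
- cycle 3: 2 × 21 = 42 days after the first dose
- cycle 6: 5 × 21 = 105 days
- cycle 9: 8 × 21 = 168 days
- after cycle 9: every 2 × 42 = 84 days

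The spacing is therefore 63 days between cycles 3, 6 and 9, and 84 days afterwards. For a course of L days starting at a uniformly random time, with draws every G days, P(course covers a draw) = min(1, L/G).

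| Course length L | G = 63 | G = 84 |
|---|---|---|
| 28 days (shortest taper alone) | 28/63 = 0.44 | 28/84 = 0.33 |
| 42 days | 42/63 = 0.67 | 42/84 = 0.50 |
| 56 days | 56/63 = 0.89 | 56/84 = 0.67 |

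The course lengths above 28 days are assumptions. The table also assumes that draws stay on schedule.

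**4. How the bias arises.** Suppose a share f of the toxicity group's on-treatment samples is drawn on steroids, and steroids shift the marker by s. With no true link between marker and toxicity, the expected difference between the groups is f × s. The documents give neither f nor s, so the size of the bias cannot be calculated.

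**5. Which samples are exposed?** Exclusion criterion 2 bars systemic steroids at entry, and tissue is archived from before treatment (Section 6.2.1). The exposed material is on-treatment and progression blood, optional progression biopsies, and any later plasma substituted for baseline in the exosome sequencing (Section 6.2.3).

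**The case against.** The strongest reply is that nothing is lost. Medication is in the clinic database of a single-center trial, and Section 9.2 says "Linkage to patient identity will be possible only after accessing a password-protected database", so re-linkage is possible. A reader might infer from item 6 that on-steroid samples can never be identified, or that adjustment is impossible. The documents do not support that: chart abstraction could recover the dates. What stands is that no section plans this step or says how the results would be used.

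The overlap model is also open to attack. Draws follow dosing, and Table 2 holds drug for these same toxicities, so steroid timing and draw timing are dependent. Restarting during a taper raises the chance of overlap. Permanent discontinuation, required for several Grade 3-4 events, ends the cycle-linked draws and lowers it. Many patients would not reach cycle 9 at day 168, since Section 3.1.7 expects most metastatic IBC patients to progress within 4 months. The net direction is unknown, so the probabilities are illustrations only.

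It is tempting to turn them into a patient count. With an assumed steroid-use rate of 10-20%, 50 × 0.10 × 0.44 = 2.2 and 50 × 0.20 × 0.67 = 6.7. The documents give no such rate and not all 50 patients stay at risk across the draws, so that range should not be cited as a finding.

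Finally, a steroid flag alone does not settle the toxicity question. A sample drawn after onset cannot show prediction, with or without steroids. This objection stands and shapes the fix.

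**Conclusion.** The point holds as a data-capture and analysis gap with a cheap remedy. Followed as written, the plan leaves on-treatment and progression samples drawn on steroids unidentifiable from the study database, and Section 7 has no provision for them. Because on-treatment steroid use is tied to suspected immune toxicity, the exploratory biomarker-safety and biomarker-change analyses may be confounded.

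A reader might go further and infer that steroid effects will be reported as MK-3475 or toxicity biomarkers. The documents support a risk, not that outcome: the clinic record exists and recorded adverse events are a partial guide. The primary disease control rate, the two-stage decisions and the toxicity stopping rule do not use these samples.

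The size is unknown. The 0.33 to 0.44 illustration rests on a 28-day course, a uniformly random start, and draws kept at 84-day or 63-day spacing. The conclusion does not depend on those figures. It rests on item 6 of Section 9.1, on steroids altering at least some of the immune readouts, and on the flow chart marking medication review at screening only.

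**What to change.** **Data.** Amend Section 9.1, item 6, and the flow chart. Record in REDCap, through the last research draw, the start date, stop date and daily dose of systemic corticosteroids and other immunosuppressants. Other concomitant drugs can stay in the clinic record. Flag each research sample as on or off steroids, and include the flag in the de-identified data. Confirm that adverse event onset dates are captured, since Section 9.1 does not mention them.

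**Analysis (Section 7).** Prespecify that:
- on-treatment biomarker analyses are reported with a time-varying steroid indicator;
- a sensitivity analysis omits on-steroid samples;
- biomarker-toxicity analyses use samples drawn before toxicity onset.

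On-steroid samples should not simply be dropped from the main biomarker-safety analysis. While treatment continues they come almost entirely from patients with suspected toxicity, so dropping them would remove data according to the outcome.

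**Cost.** A small amount of transcription for drugs already in the clinic record, and one additional analysis. No clinical rule changes.
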